## **Study Protocol**

### **Description**

College students are currently experiencing unprecedented stress during the COVID-19 pandemic and a unique learning environment with many courses being taught online.

Mindfulness practices and physical activity have previously been demonstrated to help reduce stress and anxiety among college students. This study will examine short breathing meditations paired with Fitbit technology in order to help students practice mindfulness and track physical activity. Measures including heart rate, physical activity, sleep patterns, as well as assessments of well-being and anxiety levels will be examined. Participants will be current undergraduate and graduate students at Winthrop University. The anticipated sample size is 20 subjects (10 in the experimental group and 10 in the control group). The anticipated sample size for interviews is 5 subjects.

### **Design and Methods**

Participants will be divided into two groups – experimental and control group.

The experimental group will spend two weeks wearing the Fitbit for as close to 24 hours each day (including during sleep), except when showering or charging the device. For the second week, participants will also use the Fitbit meditation app, Relax, to complete a 5-minute breathing meditation once a day, every day for one week. The Fitbit will measure physical activity and record physiological data. Following the two weeks, a subset of the experimental group will participate in semi-structured interviews to discuss their experience.

The control group will wear the Fitbit for 2 weeks, but will not complete any meditation. They will be offered the opportunity to participate in the meditation activities after the study is complete.

Participants will complete the HADS survey, MHC-SF survey, UMC Penn State Worry Questionnaire, and MAAS survey, at baseline and at the end of the second week of the program (please see attached for all surveys). They will also complete a pre-program survey at baseline and a post-program survey (including demographic information and experience with COVID-19) after the 2-week program (please see attached surveys). All surveys will be administered via email and completed via Qualtrics.

Additionally, a subset of participants will be invited to complete semi-structured interviews with the research team about their experience (please see attached for interview questions). Each interview will have 6 questions, but the total number of questions may vary depending on the follow-up questions prompted by the subjects' responses. The estimated time to complete the interview is 30 minutes.

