### **Statistical Analysis Plan (SAP)**

Survey data collected via Qualtrics (Provo, UT). Fitbit data downloaded from participants' Fitbit accounts into Microsoft Excel for analysis. Statistical analysis using R ([R Core Team, 2021](#), R Version 4.1.0, Vienna, Austria). Data combined across all three cohorts for all analysis. All data assessed for normality using the Shapiro-Wilk test, and  $p > 0.05$  for all samples. Fisher's exact test used to analyze categorical variables (race, class, sex), and t-tests used to analyze continuous variables (age, BMI) between control and treatment groups in demographic data. Paired t-tests used to compare baseline/post-study survey data and week 2/week 1 Fitbit data, and t-tests used to compare control and treatment groups at each time point. All values are reported as mean  $\pm$  standard deviation (SD). To examine the mean differences between groups, 95% confidence intervals (CI) were used ([Cumming, 2014](#)).

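### The plan does not say how participants are assigned to groups, and its unadjusted t-tests could not separate a selection difference from a meditation effect

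*Combined protocol and SAP*

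**What the plan says.** The allocation rule in Design and Methods is one sentence: "Participants will be divided into two groups". The text does not say who assigns, by what sequence, whether the assignment is concealed, or whether it comes before or after the baseline surveys. For controls it adds "The control group will wear the Fitbit for 2 weeks, but will not complete any meditation" and "They will be offered the opportunity to participate in the meditation activities after the study is complete".

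The Description gives the size: "The anticipated sample size is 20 subjects (10 in the experimental group and 10 in the control group").

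The SAP pools everyone: "Data combined across all three cohorts for all analysis". For outcomes it plans paired tests over time within groups and "t-tests used to compare control and treatment groups at each time point". For comparability it says "Fisher's exact test used to analyze categorical variables (race, class, sex), and t-tests used to analyze continuous variables (age, BMI) between control and treatment groups". It has no baseline-adjusted between-arm comparison, no between-arm test of change and no cohort term.

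**The concern.** An unadjusted post-study t-test estimates the effect of meditation only if the arms would otherwise have been alike on average. Random assignment secures that; the rule as written does not require it. A team could assign by stated preference, sign-up order or cohort and still follow the plan exactly.

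The surveys measure self-reported anxiety, worry, well-being and mindfulness. Interest in meditation could plausibly be related to all of these. If cohorts ran at different times and assignment followed cohort, differences in pandemic circumstances would also fall between the arms. Either difference would pass straight into the post-study mean difference and its 95% confidence interval. At stake is whether the main contrast can be read as an effect of meditation or only as an association.

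**Working it through.** **The plan's own figure.** The stated size adds up (10 + 10 = 20). It cannot be reproduced further, because no effect size, SD, power or significance level is given.

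**Inputs.** From the Description: n = 10 per arm. From the SAP: two-sample t-tests, so df = 10 + 10 − 2 = 18. Assumed: two-sided 5% level (the SAP gives only 95% intervals), no true meditation effect, and a selection gap s in SD units. No document supplies a gap, so a range is shown.

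**Post-study t-test when the gap persists.** The noncentrality is s × √(n/2) = s × √5 = 2.236 s. The chance of a significant result is P(|T| > 2.101), with T noncentral t on 18 df.

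| Assumed gap s | Noncentrality | Significant with no true effect |
|---|---|---|
| 0 | 0 | 5.0% |
| 0.2 SD | 0.447 | 7.1% |
| 0.3 SD | 0.671 | 9.7% |
| 0.5 SD | 1.118 | 18.5% |
| 0.8 SD | 1.789 | 39.5% |

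**Would the planned baseline tests reveal the gap?** A baseline survey t-test has the same n, so by the same formula it detects a 0.5 SD gap 18.5% of the time and a 0.8 SD gap 39.5% of the time. The tests on age and BMI have that same power for a gap in age or BMI, but do not measure a gap in the outcome scores.

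**Both tests together, and the paired tests.** These come from 40,000 simulated trials per setting with no treatment effect. Ranges cover assumed baseline–post correlations ρ of 0.5 and 0.7.

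| Result | s = 0 | s = 0.5 | s = 0.8 |
|---|---|---|---|
| Gap persists: post-study significant, baseline not | 3–4% | 9–11% | 13–17% |
| Gap persists: paired test in the selected group | about 5% | about 5% | about 5% |
| Selected group regresses to the mean: post-study test | about 5% | 8–12% | 14–23% |
| Selected group regresses to the mean: its paired test | about 5% | 8–11% | 14–21% |

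A between-arm comparison of change stays at about 5% when the gap is stable, but the SAP does not plan one.

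**What randomisation would and would not do.** With s = 0 every simulated test stays near 5%. Chance imbalance remains: the SD of the baseline standardised difference is √(2/10) = 0.45, and it exceeds 0.5 SD in either direction about 26% of the time.

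**What baseline adjustment would do if assignment was not random.** Under regression to the mean, adjustment removes the gap. Under a stable gap it leaves s × (1 − ρ): for s = 0.5, that is 0.5 × 0.5 = 0.25 SD at ρ = 0.5 and 0.5 × 0.3 = 0.15 SD at ρ = 0.7. It reduces the bias but does not turn a selected comparison into a randomised one.

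**The case against.** A reader might infer that students chose their own group, or that assignment is known to be non-random. The documents support neither. They never say that participants choose, and the later offer of meditation to controls fits assignment by the study team equally well. Part of the document was also removed before review and the attachments are not shown, so silence is not proof. This stands, and the point is therefore conditional. But Design and Methods reads as complete, it is where an allocation method belongs, and none is there.

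A reader might also infer that demographic tests are the only safeguard. They are not. The surveys are taken at baseline, so testing the arms at each time point includes baseline anxiety, worry, well-being and mindfulness. A stable gap also leaves the within-group paired tests undistorted. This stands too. The protection is weak, though: the baseline tests usually miss gaps of this size, the plan attaches no consequence to a positive one, and the paired tests do not compare the arms.

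The percentages in the first table are t-test power at assumed gaps, read in isolation. Counting only trials where the baseline test is also non-significant roughly halves them or more at 0.5 and 0.8 SD. That is fair, but the result remains above the 3–4% seen with no gap.

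Finally, the plan states no causal claim, and parts of the SAP read as though data already exist: it reports Shapiro-Wilk results above 0.05 for every sample and refers to three cohorts. Writing randomisation into the protocol for a cohort already assigned some other way would misdescribe it. This changes the remedy, not the defect.

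**Conclusion.** The concern holds in conditional form. The plan describes no random or concealed assignment and no allocation within cohorts, and its between-arm tests are unadjusted. If groups were formed by choice, convenience or cohort, a significant post-study difference could reflect selection. It does not follow that it would, or that selection occurred.

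The size depends on assumed gaps. At 0.3, 0.5 and 0.8 SD, persisting to the end of the study, the false-positive rate is about 10%, 18.5% and 39.5% against 5%. It is lower if the gap shrinks by regression to the mean. These figures rest on 10 per arm and a two-sided 5% level. The direction of any bias is unknown.

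This is more than a reporting gap, because better methods are available from data the plan already collects. It should be changed before the between-arm results are interpreted.

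**What to change.** 1. **Cohorts not yet assigned.** Replace the allocation sentence with: *Within each cohort, participants will be randomised 1:1 to the experimental or control group from a computer-generated permuted-block list. Each assignment is released only after that participant's baseline surveys are submitted.* Cost: one sentence and a list, with no extra participants or visits.
2. **Cohorts already assigned.** State how the groups were actually formed. If this was random, give the sequence, the concealment and any stratification by cohort. Do not add a randomisation statement after the fact.
3. **All cohorts.** Replace the unadjusted post-study t-tests with a linear model for the post-study score containing arm, baseline score and cohort. For Fitbit data, use the week 2 value with the week 1 value as covariate. Report the adjusted difference with its 95% confidence interval. With 20 participants and three cohorts, the residual df fall from 18 to 20 − 5 = 15 (intercept, arm, baseline, two cohort terms). If a whole cohort went to one arm, the cohort term cannot fully separate the two, and the report should say so.
4. **If any cohort was not randomised.** Word the between-arm conclusion as an association, since adjustment can leave part of a stable gap in place.

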### **Statistical Analysis Plan (SAP)**

Survey data collected via Qualtrics (Provo, UT). Fitbit data downloaded from participants' Fitbit accounts into Microsoft Excel for analysis. Statistical analysis using R ([R Core Team, 2021](#), R Version 4.1.0, Vienna, Austria). Data combined across all three cohorts for all analysis. All data assessed for normality using the Shapiro-Wilk test, and  $p > 0.05$  for all samples. Fisher's exact test used to analyze categorical variables (race, class, sex), and t-tests used to analyze continuous variables (age, BMI) between control and treatment groups in demographic data. Paired t-tests used to compare baseline/post-study survey data and week 2/week 1 Fitbit data, and t-tests used to compare control and treatment groups at each time point. All values are reported as mean  $\pm$  standard deviation (SD). To examine the mean differences between groups, 95% confidence intervals (CI) were used ([Cumming, 2014](#)).

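### The between-arm t-tests leave out the baseline (or week 1) value already collected, which costs precision at 10 per arm if that value correlates with the outcome above roughly 0.26 to 0.3

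*Combined protocol and SAP*

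**What the plan says.** The Statistical Analysis Plan section describes two kinds of outcome test. Within participants: "Paired t-tests used to compare baseline/post-study survey data and week 2/week 1 Fitbit data". Between arms: "t-tests used to compare control and treatment groups at each time point". For estimation it adds: "To examine the mean differences between groups, 95% confidence intervals (CI) were used". It does not say whether those mean differences are of end values or of changes from baseline.

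On cohorts it says "Data combined across all three cohorts for all analysis". Cohorts are mentioned nowhere else in the available text, and no cohort term or stratification is named.

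The Design and Methods section has the four questionnaires completed "at baseline and at the end of the second week of the program", so a baseline score is available for each of them. On allocation it says "Participants will be divided into two groups" and gives no method and no arm counts by cohort. The Description section gives the size: "The anticipated sample size is 20 subjects (10 in the experimental group and 10 in the control group").

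**The concern.** The arm comparison is the one that bears on the meditation effect. As written, it tests the post-study (or week 2) values without using what is known about each participant beforehand. When the same scale is measured twice in the same person, part of the spread in the second measurement is usually predictable from the first. A t-test on the end value leaves that part in the error term. The paired tests do use the earlier value, but they compare time points rather than arms, so they do not fill the gap.

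With 20 participants, the width of the between-arm interval largely decides what can be learned. A method that narrows it without new data is worth having.

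Pooling the cohorts raises a second, conditional question: whether differences between cohorts could be mistaken for a difference between arms.

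**Working it through.** **Inputs.** From the documents: 10 per arm, 95% intervals, three cohorts, and measurements before and after. Assumed, because the documents do not give them: two-sided 5% test level (taken from the 95% interval), outcome SD 1, effect 1 SD, correlation r from 0.2 to 0.8, cohort sizes 7/7/6. The sample size of 20 comes with no effect size, SD or power, so there is no planned figure to reproduce.

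**1. Planned t-test.** Variance of the arm difference = 2/10 = 0.20, with 18 df. The expected 95% half-width is 2.101 × √0.20 = 0.94 SD. Power for 1 SD is 56.2% (noncentral t).

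**2. Linear model with arm and baseline.** Variance = 0.20 × (1 − r²) × (1 + 1/(20 − 4)) = 0.20 × (1 − r²) × 17/16, with 17 df. The factor 17/16 is the average price of chance baseline imbalance. At r 0.6 this is 0.20 × 0.64 × 1.0625 = 0.136, so the half-width is 2.110 × √0.136 = 0.78 SD.

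**3. Comparison of change scores.** Variance = 0.20 × 2(1 − r), with 18 df. At r 0.6 this is 0.16. It equals the t-test's 0.20 at r 0.5 and is larger below that.

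Power for a 1 SD effect from these formulas:

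| r | t-test on end value | change score | baseline-adjusted |
|---|---|---|---|
| 0.2 | 56% | 39% | 55% |
| 0.4 | 56% | 49% | 61% |
| 0.6 | 56% | 66% | 72% |
| 0.8 | 56% | 92% | 93% |

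Simulation with near-even arms (4:3, 3:4, 3:3) and no cohort differences agrees within about a point, with about 73% for the adjusted model at r 0.6. Simulated mean 95% interval width is 1.85 SD for the t-test, against 1.53 SD (r 0.6) or 1.15 SD (r 0.8) with baseline.

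**4. Break-even.** The adjusted interval matches the t-test's when 2.110² × (1 − r²) × 17/16 = 2.101². Then 1 − r² = 0.933 and r = 0.26. Given simulation error and the dependence on balance, about 0.26 to 0.3 is a fair statement.

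**5. Cohort: when would pooling bias the arm difference?** Suppose cohort means rise by a constant step. The t-test bias is then step × (mean cohort index, experimental minus control), with cohorts indexed 0, 1, 2.
- Equal arm ratios in every cohort: difference 0, so no bias whatever the step.
- Moderately uneven (3:4, 3:4, 4:2): 1.1 − 0.8 = 0.30. At 0.5 SD per step, bias is 0.15 SD and type I error about 4%.
- Very uneven (2:5, 3:4, 5:1): 1.3 − 0.6 = 0.70. At 0.5 SD per step, bias is 0.35 SD and type I error about 9%. An imbalance this large arises in about 10% of random splits.
- Arms drawn at random over the cohorts: type I error 5.0% at every step tried, with no bias on average.

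**6. Does a cohort term improve precision?** Random splits, r 0.6, 1 SD effect, constant cohort steps:

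| Step (SD) | t-test | baseline | baseline and cohort |
|---|---|---|---|
| 0.25 | 54% | 72% | 67% |
| 0.5 | 50% | 71% | 67% |
| 0.75 | 43% | 69% | 65 to 66% |

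The gain over the t-test comes from baseline. Adding cohort lowers power somewhat, even when cohorts truly differ in level.

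**The case against.** **The t-tests are valid as they stand.** If allocation was random, they hold their 5% error rate. This stands: the point concerns precision, not validity.

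**The gain depends on a correlation the documents do not give.** This also stands. At r 0.2 adjustment loses about 1 point of power, so it would be wrong to say that precision is lost unconditionally. Moderate correlation is plausible for the same scale repeated two weeks apart, but that is an assumption.

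**The interval may already use baseline.** If "To examine the mean differences between groups, 95% confidence intervals (CI) were used" refers to changes, it does. That ambiguity is real. It does not alter the named t-tests, and a change-score comparison is less precise than baseline adjustment across the range examined, and less precise than the plain t-test when r is below 0.5.

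**The analysis may already be done.** The SAP section is partly in the past tense and reports a normality result. If so, the remedy shrinks to a labelled sensitivity analysis.

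**Stronger readings to avoid.** A reader might infer that pooling has biased the arm comparison. That needs cohort means that differ and arm ratios that differ by cohort, and the documents show neither. A reader might also infer that allocation was not random. The available text gives no method, which is not evidence either way. Finally, a reader might conclude that cohort must be in the main model. At 20 participants that is a trade-off that the precision results do not favour.

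**Conclusion.** The point holds for the between-arm comparison. The plan leaves out a covariate it already collects, and with 10 per arm this costs precision if r is above about 0.26 to 0.3. For a 1 SD effect, the loss against a baseline-adjusted model is about 5 points of power at r 0.4, 17 at r 0.6 and 37 at r 0.8. At r 0.2 the planned test is about 1 point better. These sizes rest on the assumed effect, the assumed range of r and approximately normal outcomes.

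The pooling of cohorts is an open question, not a demonstrated bias. Arm counts by cohort would show whether ratios differ enough for it to matter.

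**What to change.** For the between-arm comparison, analyse the post-study (or week 2) value by a linear model with arm and the baseline (or week 1) value as terms. Report the adjusted arm difference with its 95% interval beside the unadjusted t-test. Fix the terms in advance rather than choosing them by result. State whether the mean differences in the interval sentence are of end values or changes.

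Report arm counts by cohort. Add cohort (three levels) only as a sensitivity analysis. It costs two more residual degrees of freedom, about 1 to 2 points of power with near-even arms, and about 4 to 6 under random splits, even when cohorts differ by constant levels.

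Cost of the main change: no new data, one residual degree of freedom (18 to 17), and about 1 point of power if r is near 0.2. If outcome data have already been examined, keep the t-tests as stated and label the adjusted model post hoc.

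### Does the all-pass Shapiro-Wilk statement undermine the planned t-tests at about 10 per group?

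*Combined protocol and SAP*

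**What the plan says.** The Statistical Analysis Plan (SAP) states "All data assessed for normality using the Shapiro-Wilk test" and adds that p exceeded 0.05 "for all samples". It names neither the quantity tested (raw values by group and time point, pooled values or within-person differences) nor the number of samples.

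The tests follow in the same paragraph. For demographics: "t-tests used to analyze continuous variables (age, BMI) between control and treatment groups". For change over time: "Paired t-tests used to compare baseline/post-study survey data and week 2/week 1 Fitbit data". Groups are also compared by t-test at each time point, with 95% confidence intervals for the between-group mean differences. No sentence makes any test depend on the normality result, and no linear model is planned.

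On size, the Description says "The anticipated sample size is 20 subjects (10 in the experimental group and 10 in the control group". The SAP adds "Data combined across all three cohorts for all analysis" but gives neither the cohort sizes nor a final n.

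**The concern.** The normality sentence stands directly before the t-tests and is the only support offered for them, so it is natural to read it as their justification. Four things then look wrong.

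- With about 10 values, Shapiro-Wilk misses most moderate skew, so a pass shows little.
- Many samples are checked at the 5% level. Even normal data would often produce at least one failure, and no route is given for that case.
- A paired t-test relies on the distribution of the within-person differences, and the SAP does not say that these were checked.
- The sentence reports an outcome inside a plan, which raises the question whether the tests were settled after the data were seen.

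At stake is the error rate of the p-values, above all for the paired tests. If change scores were strongly skewed, a nominal 5% test on 10 people could reject a true null about twice as often as stated.

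**Working it through.** **Inputs.** From the documents: 10 per group (Description, anticipated only); four scales at two time points (Design and Methods: "Participants will complete the HADS survey, MHC-SF survey, UMC Penn State Worry Questionnaire, and MAAS survey, at baseline and at the end of the second"); at least three Fitbit domains (Description: "Measures including heart rate, physical activity, sleep patterns") over two weeks; age and BMI (SAP). The distributions and correlations below are assumptions. The stated all-pass result cannot be reproduced, because the documents give no data, no count of samples and no final n.

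**1. Number of samples, if each group and time point is tested separately.**
- Surveys: 4 × 2 × 2 = 16.
- Fitbit: 3 × 2 × 2 = 12, running total 28.
- Age and BMI: 2 × 2 = 4, running total 32.

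**2. Chance that all k samples pass when all are exactly normal and independent: 0.95^k.**

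| k | What is tested | Chance all pass |
|---|---|---|
| 7 | differences for 7 outcomes, groups pooled | 0.70 |
| 14 | differences for 7 outcomes, by group | 0.49 |
| 16 | survey values | 0.44 |
| 28 | survey and Fitbit values | 0.24 |
| 32 | those plus age and BMI | 0.19 |

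Simulated correlation between time points (0.7 to 0.9) and between measures (0.3 to 0.5) changes this little: 0.20 to 0.24 for k = 32. The answer depends mainly on a count that the SAP does not state. At none of these counts is an all-pass result implausible.

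**3. Power of Shapiro-Wilk at the 5% level (simulated).**

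| Assumed shape | n = 10 | n = 20 | n = 30 |
|---|---|---|---|
| Gamma, skewness 1 | 14% | 30% | 44% |
| Chi-square(4) | 24% | 53% | 75% |
| Exponential | 44% | 84% | 97% |

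At the anticipated size a pass says little. The pooled n is unknown, so the right column is unknown too.

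**4. Type I error of nominal 5% t-tests at n = 10 (simulated).**

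| Assumed shape | Two-sample, same shape in both groups | Paired, differences of this shape with mean zero |
|---|---|---|
| Gamma, skewness 1 | 4.9% | 6.4% |
| Chi-square(4) | 4.4% to 4.7% | 7.6% |
| Exponential | 4.2% to 4.7% | 9.9% to 10.2% |
| Lognormal, sigma 1 | 3.4% | 16.2% |

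The paired column assumes that the differences themselves have the stated shape. Skewed scores do not imply that. If the before and after scores are exchangeable under the null, their difference is symmetric however skewed each score is. Simulating exponential and chi-square(4) scores of that kind, with correlation 0.5 to 0.7, gives a paired-test error of 2.7% to 4.6%, depending on how the correlation is built. That is conservative.

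**5. What a replacement would change.** A permutation p-value for the between-group comparisons agreed with the t-test at the 5% level in about 99% of simulated null trials. At 10 per group and a 1.3 SD effect, power was 78.5% by permutation and 78.7% by t-test. The addition costs almost nothing and changes almost nothing. It also leaves the paired tests, the only ones at possible risk, as they are.

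**The case for a change.** The strongest reply is that passing the check does not protect the paired tests even when it is applied to the differences. Among simulated samples whose differences passed Shapiro-Wilk, the type I error was 8.6% for chi-square(4) and 12.7% for exponential differences, higher than without screening. The quantity tested also matters. In an assumed example where 20% of participants shift by 1 SD and the rest hardly move, raw before and after values both passed in 92% of runs, but the differences passed in only 25%. A sentence that gives false comfort is arguably worth removing.

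This stands as a warning against reading p above 0.05 as proof of normality. It does not show that the planned tests are wrong. The inflation again needs strongly skewed change with zero mean, for which the documents give no evidence either way. Because the SAP does not name the quantity tested, the claim that the wrong one was used is unproven; the SAP only fails to say that differences were checked. Checking assumptions after data collection is ordinary practice, so reporting the outcome does not show that the tests were chosen afterwards. The fallback complaint and the hindsight complaint also pull apart: if the sentence is an observed result, no failed sample exists that would need a fallback.

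**Conclusion.** No change to the plan follows. The check is weak at the anticipated size (power about 24% to 44% for the two skewed shapes used throughout), and the all-pass statement should carry little weight. But the t-tests are run with or without that sentence, and removing it would alter no estimate, interval or p-value. The only confidence intervals planned are between groups. With the same distributional shape in both groups, those comparisons hold a 3.4% to 4.9% error rate at n = 10.

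The paired tests would be anti-conservative, at roughly 6% to 16%, only if the change scores are skewed around a zero mean. With exchangeable scores they are at 2.7% to 4.6%. The documents do not settle which applies.

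What is left is a reporting gap that analysts can fill when they write up: the quantity tested, the number of samples and the actual n. These conclusions rest on the anticipated 10 per group and on assumed distributions. A larger pooled n would make the normality check more informative.

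### No planned test compares change between arms or adjusts the follow-up comparison for baseline, and the SAP does not say which test decides whether meditation worked

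*Combined protocol and SAP*

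**What the plan says.** The Statistical Analysis Plan gives two families of outcome test. Over time: "Paired t-tests used to compare baseline/post-study survey data and week 2/week 1 Fitbit data". Between arms: "t-tests used to compare control and treatment groups at each time point". It adds: "To examine the mean differences between groups, 95% confidence intervals (CI) were used". It does not say whether the paired tests are run by arm, whether the interval is for follow-up values or for changes, or which result carries the conclusion. No group-by-time term, between-arm test of change or baseline covariate appears.

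The design would support more. Under Design and Methods, both arms complete the surveys at baseline and at the end of week 2, and both wear the device in week 1, before any meditation. The comparator is clear: "The control group will wear the Fitbit for 2 weeks, but will not complete any meditation". On allocation, the section says only "Participants will be divided into two groups". The Description section anticipates 20 participants, 10 in each group.

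**The concern.** The control group is there to show what happens over two weeks without meditation. A paired test within the experimental arm discards that information. Its result mixes meditation with anything that moves both arms, such as the academic calendar or regression to the mean and, for the surveys, two weeks of wearing the device. If significance in one arm and not in the other is read as an effect, the error rate for the meditation question is not held at 5%.

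The between-arm t-test at the end of week 2 is the right kind of contrast, but it ignores where each participant started. With 10 per arm the groups can easily differ at baseline. Because the text does not describe random allocation, such a difference need not be chance. The estimate then depends on how alike the groups were at the start, and its interval may be wider than the collected data allow.

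**Working it through.** The plan gives no power, effect size or SD, so there is no figure of its own to reproduce.

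**Inputs.** From the documents: 10 per arm. Assumed: two-sided 5% (in line with the 95% CI), normal data, SD 1 at both times, pre-post correlation r, shared trend, effect size and baseline difference.

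**1. Paired test in the experimental arm, no meditation effect.** The SD of a change is √(2(1−r)), so dz = trend/√(2(1−r)). The noncentrality is dz×√10 on 9 df.

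| r | dz, 0.5 SD trend | noncentrality | significant | significant, 0.2 SD trend |
|---|---|---|---|---|
| 0.2 | 0.395 | 1.25 | 20% | 7% |
| 0.3 | 0.423 | 1.34 | 22% | 8% |
| 0.5 | 0.500 | 1.58 | 29% | 9% |
| 0.7 | 0.645 | 2.04 | 45% | 11% |
| 0.8 | 0.791 | 2.50 | 61% | 15% |

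In simulated null trials with a 0.5 SD shared trend, the pattern of significant in the experimental arm but not in the control arm occurs in 21% (r = 0.5) and 25% (r = 0.7). A between-arm test of change and the follow-up t-test both stay at about 5%.

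**2. Precision at follow-up, true effect 0.8 SD.** For the t-test, the standard error is √(2/10) = 0.447 and the noncentrality 0.8/0.447 = 1.79 on 18 df. Power is 39.5% and the mean 95% CI half-width 0.93 SD. For ANCOVA the residual SD is √(1−r²) on 17 df; power and half-width come from 40,000 simulated trials per setting.

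| r | √(1−r²) | ANCOVA power | mean half-width (SD) |
|---|---|---|---|
| 0.2 | 0.980 | 39% | 0.94 |
| 0.3 | 0.954 | 41% | 0.91 |
| 0.5 | 0.866 | 48% | 0.83 |
| 0.7 | 0.714 | 63% | 0.68 |
| 0.8 | 0.600 | 78% | 0.57 |

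The two methods break even near r = 0.25. The gain becomes worthwhile at about r = 0.5.

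**3. Baseline imbalance.** Under random allocation the difference in baseline means has SD 0.447, so P(|difference| > 0.5 SD) = 2×[1 − Φ(0.5/0.447)] = 26%. A 0.5 SD difference shifts the expected follow-up difference by r×0.5, that is 0.25, 0.35 and 0.40 SD at r = 0.5, 0.7 and 0.8.

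If that baseline difference is systematic and carries forward as r×0.5, the t-test rejects a true null in about 8%, 11.5% and 14% of trials, against 5% for ANCOVA. If the groups instead differ by a stable 0.5 SD that persists in full, the t-test is biased by 0.50 SD and ANCOVA by (1−r)×0.5 = 0.25, 0.15 and 0.10 SD. The t-test then rejects a true null in 18% to 19% of trials and ANCOVA in roughly 6% to 9%.

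**The case against.** The strongest reply is that the plan already holds a valid analysis. Under random allocation the follow-up t-test keeps its 5% level, and the paired tests do harm only if someone treats them as proof of effect. Both points are true. But the SAP leaves that reading open, and a valid test can still be imprecise and sensitive to imbalance.

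Second, the CI sentence could mean differences in change, in which case a suitable estimate is already planned. It says neither change nor adjustment, and it follows the time-point t-tests, so differences in group means is the more natural reading. The ambiguity itself needs resolving.

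Third, t-tests at each time point include baseline, so imbalance would be seen. Seeing it does not remove it from the follow-up estimate.

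Fourth, if allocation was not random, ANCOVA is not the only candidate. Under a stable group difference the between-arm difference in change is unbiased and ANCOVA is not. This stands, and it is why that contrast belongs in the plan as a sensitivity analysis. ANCOVA still does better than the planned t-test in both scenarios at r of 0.5 to 0.8.

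Finally, 20 is an anticipated number, and the SAP refers to three cohorts: "Data combined across all three cohorts for all analysis". If there were 30 per arm (an assumption), chance imbalance above 0.5 SD would fall from 26% to 5% and t-test power would rise to 86%. The paired-test problem would worsen, from 29% to 75% at r = 0.5 with a 0.5 SD trend.

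**Conclusion.** The concern holds and should be fixed. That no decisive comparison, between-arm test of change or baseline adjustment is listed can be read directly from the SAP and needs no assumption. The size of the harm does rest on assumptions. A false signal from the paired test ranges from 7% (0.2 SD trend, r = 0.2) to 61% (0.5 SD trend, r = 0.8). The precision lost by ignoring baseline runs from nothing at r near 0.25 to a CI about 1.6 times as wide as necessary at r = 0.8 (0.93/0.57). The trial is not unanalysable, because an unadjusted between-arm comparison exists. As written, though, its conclusion could rest on a test that does not isolate meditation.

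**What to change.** For each outcome, name one effect analysis: a linear model of the end-of-week-2 survey score on arm and baseline score, and of the week-2 Fitbit value on arm and week-1 value. Report the adjusted mean difference with its 95% CI. Keep baseline values and within-arm changes by arm as description only.

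Interpretation should follow how the groups were formed. If allocation was not random, say that adjustment reduces bias but does not remove it, and add the between-arm difference in change as a sensitivity analysis. If each cohort contains both arms, which the text does not say, cohort can be added in a further sensitivity analysis.

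The SAP already reports a normality finding ("All data assessed for normality using the Shapiro-Wilk test"). If outcome data have been examined, label the new analysis post hoc.

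The cost is SAP wording and one linear model per outcome in R. No new data are needed. Residual degrees of freedom fall from 18 to 17, and a three-level cohort term would take two more.
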